10.4 Description of Statistical Methods

10.4.1 General Approach

Statistical comparisons will be performed using two-sided significance tests and two-sided confidence intervals. We will begin all analyses with descriptive summary statistics and graphical displays of all variables, with attention to assessing balance in these characteristics by intervention group, and with assessment of the distribution of variables, relevant to the choice of statistical tests.

10.4.2 Analysis of the Primary Efficacy Endpoint(s)

6MWD

We will assess the difference in 6MWD by calculating difference scores for each participant and comparing the intervention and usual care groups with an independent group t-tests allowing for unequal variances. We will also regress 3-month 6MWD on a binary indicator of treatment group, with adjustment for baseline 6MWD and the stratification factor (enrollment site). While randomization should obviate the need for additional adjustment, we will explore whether adjustment for participant-level characteristics (e.g., demographic factors or referral to ambulatory CR) is necessary, using the change-in-estimate criterion. We realize that engagement with the mHealth-CR program may also affect attendance and engagement with structured ambulatory CR programs. We intend to explore this as a mediator of the effect of assignment to the intervention arm. We will use structural equation models to estimate the direct and indirect effects of mHealth, where the direct effect is that of mHealth-CR on the 6MWD, and the indirect effect is mediated through attendance at structured ambulatory CR.

Engagement

We hypothesize that (1) among participants offered mHealth-CR, there will be distinct trajectories of engagement (e.g., sustained engagement, disengagement, reengagement, deteriorating engagement); and (2) there will be significant differences in participant characteristics among these groups. While our aim is largely exploratory (given the paucity of data on mHealth-CR engagement), we will test whether the following characteristics are significant: age (≥ 80 years), sex, race/ethnicity, comorbidity burden (≥ 2 chronic medical conditions), frailty, social support (based on living alone), cognitive impairment (based on Mini-Cog), and depressive symptoms (based on PHQ-8). We selected these factors based on literature related to engagement in other technologies. We will conduct latent class analysis to identify profiles of engagement and explore whether these factors indicate membership in a class; these models use maximum likelihood estimation,

CONFIDENTIAL

This material is the property of the NYU School of Medicine and Langone Medical Center. Do not disclose or use except as authorized in writing by the study sponsor

implemented with the iterative EM algorithm, to identify a latent class solution for the set of indicators. We will evaluate model fit using the G^2 statistic and compare models with the likelihood-difference test for nested models and the Akaike and Bayesian information criteria (AIC, BIC) for non-nested models. While we have identified four potential classes a priori, we will use the parametric bootstrap likelihood ratio test to select the optimal number of classes supported by the data in conjunction with the AIC and BIC. The output of the model will be a set of “item-response” probabilities giving the likelihood of a particular characteristic within each latent class, and a set of posterior predicted probabilities of latent class membership; uncertainty in predicting class membership will be summarized using the odds of correct classification (OCC) diagnostic tool.

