Statistical Analysis	
Primary endpoint (efficacy): Change in 6WMD will be assessed by calculating difference scores for each participant and comparing the intervention and usual care groups with an independent group t-test. Regression of 3-month 6MWD on a binary indicator of treatment group will also be measured, with adjustment for baseline 6MWD and the stratification factor (enrollment site).
 
Secondary endpoint (efficacy): Differences in secondary endpoints will be analyzed by the appropriate statistical test for continuous or categorical measures.
 
Primary endpoint (engagement): Measurements of engagement will use latent class analysis to identify profiles of engagement and assess trajectories.

----------------------	---

Schematic of Study Design

Flow Diagram

CONFIDENTIAL

This material is the property of the NYU School of Medicine and Langone Medical Center. Do not disclose or use except as authorized in writing by the study sponsor

1 Key Roles

[name], MPH – Principal Investigator

Leon H. Charney Division of Cardiology –NYU School of Medicine
[name]
[contact]

[name] – Sub-Investigator

Center for Cardiovascular Lifestyle Medicine – NYU Winthrop Hospital
[name]

[name] EdD, RCEP, MSN, AGNP-C – Sub-Investigator

Center for Cardiovascular Lifestyle Medicine – NYU Winthrop Hospital
[name]

[name] –Co-Investigator, Biostatistician

Department of Population Health – NYU School of Medicine
[name]
[contact]

[name] – Data Management, NYU DataCore

Department of Population Health – NYU School of Medicine
[name]
[contact]

[name], MS – Co-Investigator

Department of Geriatrics –NYU School of Medicine
[name]
[contact]

[name], EdD – Co-Investigator

Department of Population Health – NYU School of Medicine
[name]
[contact]

[name] – Co-Investigator

Leon H. Charney Division of Cardiology –NYU School of Medicine
[name]
[contact]

[name]—Yale Site Principal Investigator

Yale School of Medicine
[name]
[contact]

[name] –Yale Site Co-Investigator

Yale School of Medicine
[name]
[contact]

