Health status at 3 months will be assessed using linear regression with adjustment for baseline levels and a binary treatment indicator; if necessary, health status scores will be log-transformed to improve the approximation to normality. Activities of daily living (BADLs and IADLs) will be assessed using longitudinal models for interval scores, with indicators to incorporate time, a binary indicator of treatment group, and patient-level random effects to accommodate repeated assessments within individuals; if interval scores are not approximately normally distributed, suitable transformations will be sought. Hospital readmission and death will be evaluated using Kaplan-Meier estimates and tested with logrank statistics, as well as investigated using Cox proportional hazard models with adjustment for confounders if necessary. As with the models for the primary outcome, in each model described we will assess the need for adjustment for confounders using the change-in-estimate criterion.

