10.4.9 Multiple Comparison/Multiplicity

Not applicable as there is one primary efficacy endpoint.

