10.4.11 Exploratory Analyses

Exploratory analyses for ancillary endpoints (not primary or secondary endpoints), with rationale, are as follows:

-Mean systolic blood pressure (BP) at 3-month follow-up visit. Adequately controlled BP is an important component of secondary prevention for patients with IHD, and may be influenced by participation in mHealth-CR (mediated by direct effects of exercise, as well as by feedback from weekly home BP measurement which may influence medication management and adherence). Rather than determining a threshold for optimal BP control, which remains an area of debate, we will compare mean systolic BP in the intervention versus usual care groups at 3 months.

-Frailty. Frailty is a syndrome of increased physiologic vulnerability to stressors. In older adults with IHD,

CONFIDENTIAL

This material is the property of the NYU School of Medicine and Langone Medical Center. Do not disclose or use except as authorized in writing by the study sponsor

frailty is common and associated with a range of adverse outcomes. We will measure frailty at baseline and 3 months using the criteria described by Fried et al: unintentional weight loss (≥ 10 pounds), weak grip strength (measured by handheld dynamometer), exhaustion, slow gait, and low physical activity. Participants meeting 3/5 of these criteria will be classified as frail. Since mHealth-CR may mechanistically modulate the frailty phenotype by building muscle mass and promoting physical activity, we will analyze the number of participants in each group that transition from “frail” to “not frail” between baseline and 3 months.

-Attendance at traditional (ambulatory) CR. We will ask participants at 3 months whether they have attended ambulatory CR. Based on the study protocol, all participants will receive a referral to ambulatory CR at time of discharge. We will therefore examine the rates of attendance (rather than rates of referral) between participants in the intervention versus usual care arms. Since participants may not recall the number of sessions attended, we will count number of sessions via electronic health record (EHR) review.

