10.5 Sample Size

We will randomize 400 participants using a 3:1 allocation, resulting in 300 participants in the intervention group and 100 participants in the usual care group. While we will aim to minimize participant dropout, we include adjustment for up to 20% dropout in each arm, resulting in about 320 participants with evaluable endpoints (240 intervention, 80 usual care). We wish to be able to detect a clinically meaningful difference between groups in our primary efficacy endpoint, change in 6MWD from baseline to 3 months. A recent meta-analysis⁵⁷ found an average difference in 6MWD of about 60 meters before and after traditional CR. Perera et al. determined this degree of change in 6MWD to be clinically meaningful based on its relationship to other health status measures.⁹⁸ Minneboo et al., however, also estimated an improvement in 6MWD in a control group of approximately 35 meters.⁵⁹ We therefore require adequate power to detect a difference between groups of less than 25 meters in change in 6MWD (i.e., the difference between a 60-meter improvement in the intervention group and a 35-meter improvement in the usual care group); this is the same amount estimated by Gremeaux et al. as a minimal clinically important difference in patients with IHD.⁹⁹ Assuming a conservative standard deviation estimate of 60 meters,⁵⁷ 320 participants provide approximately 90% power to detect a difference between groups of 25 meters, using a two-sided, 0.05-level test; there is 80% power to detect a difference

CONFIDENTIAL

This material is the property of the NYU School of Medicine and Langone Medical Center. Do not disclose or use except as authorized in writing by the study sponsor

between groups as small as 22 meters. This sample size also provides at least 80% power to detect reasonable effect sizes in secondary endpoints.

While the sample size was determined to provide sufficient power to detect a clinically meaningful difference in the primary outcome of 6MWD, it enables comparisons of secondary efficacy endpoints as well. The table below shows clinically meaningful effect sizes for these outcomes, and gives the power to detect these effect sizes

CONFIDENTIAL

This material is the property of the NYU School of Medicine and Langone Medical Center. Do not disclose or use except as authorized in writing by the study sponsor

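### The plan should name the baseline- and hospital-adjusted regression as the single deciding analysis of 6MWD, and bar covariate-selected models from replacing it

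*Combined protocol and SAP*

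**What the plan says.** Section 4.2.1 defines the primary efficacy endpoint as the change in 6MWD from baseline to the 3-month visit. Section 10.4.2 first computes a difference score for each participant, "comparing the intervention and usual care groups with an independent group t-tests allowing for unequal variances". It continues: "We will also regress 3-month 6MWD on a binary indicator of treatment group, with adjustment for baseline 6MWD and the stratification factor (enrollment site". The Protocol Summary has the same pair in the same order: "Regression of 3-month 6MWD on a binary indicator of treatment group will also be measured". Neither place ranks the two.

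Section 10.4.2 then turns to further covariates: "While randomization should obviate the need for additional adjustment, we will explore whether adjustment for participant-level characteristics", with demographic factors and referral to ambulatory cardiac rehabilitation (CR) as examples, judged by the change-in-estimate criterion. Section 10.4.3 carries the criterion over to the secondary endpoints, expressly on the same footing as the primary-outcome models: "in each model described we will assess the need for adjustment for confounders using the change-in-estimate criterion". No threshold is given and the covariate list is open.

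Section 10.4.9 on multiplicity reads "Not applicable as there is one primary efficacy endpoint". Section 10.5 asks for "adequate power to detect a difference between groups of less than 25 meters in change in 6MWD".

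**The concern.** One endpoint can still be analysed in several ways. Section 10.4.9 counts endpoints and does not say which analysis of the single endpoint settles it. If the t-test and the regression fall on opposite sides of 0.05, the plan has no rule for what the trial concludes.

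The likely answer, that the t-test decides, has its own cost. Randomisation is stratified by hospital, and the t-test does not use hospital. It also fixes the coefficient of baseline 6MWD at 1, where the regression estimates it. Precision that an already planned model would usually recover then does not reach the primary result.

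Change-in-estimate is a tool for choosing confounders in observational data. In a randomised comparison it selects covariates by how far they move the treatment estimate, and the plan itself accepts that randomisation should make further adjustment unnecessary. The step is worded as exploration in 10.4.2, but nothing says that a model reached this way may not become the reported primary result.

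**Working it through.** **Inputs from 10.5:** 240 intervention and 80 usual care evaluable; SD 60 m, read as the SD of change; difference 25 m; two-sided 0.05.

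**1. The plan's own figure.** SE = 60 × √(1/80 + 1/240) = 7.746 m. 25 / 7.746 = 3.227. The noncentral t on 318 df gives 89.6%, against the stated 90% or so. At 22 m, 22 / 7.746 = 2.840 gives 80.8%, against the stated 80%. Both reproduce, and both fit an unadjusted comparison of change scores.

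**2. Regression, equal visit SDs and equal slopes.** The documents give neither the baseline/3-month correlation ρ nor visit SDs, so ρ is an assumption. With visit SD s, Var(change) = 2s²(1 − ρ) and the residual variance after baseline adjustment is s²(1 − ρ²). The ratio is (1 + ρ)/2, so the residual SD is 60 × √((1 + ρ)/2).

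| ρ | Variance ratio | Residual SD (m) | Power at 25 m |
|---|---|---|---|
| 0.5 | 0.75 | 52.0 | 96.0% |
| 0.7 | 0.85 | 55.3 | 93.7% |
| 0.9 | 0.95 | 58.5 | 91.0% |

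**3. Where the gain vanishes.** Let the 3-month SD be k times the baseline SD. In units of baseline variance, the change score has 1 + k² − 2ρk and the regression k²(1 − ρ²). With k = 1.25 and ρ = 0.8 these are 1 + 1.5625 − 2 = 0.5625 and 1.5625 × 0.36 = 0.5625. The ratio is 1, and both analyses have 89.6% power.

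**4. Where it turns negative.** Under 3:1 allocation, a common-slope regression can lose to the change score if slopes differ by arm. Assume a baseline SD of 80 m (variance 6400), slopes b₁ (intervention) and b₀ (control), and residual SD r. The pooled slope is b = 0.75b₁ + 0.25b₀. The variances of the arm difference are:
- common-slope regression: [r² + (b₁ − b)² × 6400]/240 + [r² + (b₀ − b)² × 6400]/80
- change score: the same with b replaced by 1
- regression with a centred arm-by-baseline term: r²(1/240 + 1/80) + (b₁ − b₀)² × 6400/320

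For b₁ = 0.7, b₀ = 1.0, r = 56, the pooled slope is 0.775. The regression has 3172/240 + 3460/80 = 56.5, the change score 3712/240 + 3136/80 = 54.7, and the interaction model 52.27 + 1.80 = 54.1.

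| b₁, b₀, r | Variance: regression / change / interaction | Power at 25 m |
|---|---|---|
| 0.7, 1.0, 56 | 56.5 / 54.7 / 54.1 | 91.3 / 92.1 / 92.4% |
| 0.6, 1.0, 54 | 56.1 / 52.9 / 51.8 | 91.4 / 92.9 / 93.4% |
| 1.0, 0.7, 56 | 56.5 / 59.5 / 54.1 | 91.3 / 89.8 / 92.4% |

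The loss is 0.8 and 1.5 points in the first two rows; the third row is a gain of 1.5. These rows are not calibrated to a change SD of 60 m (by arm it runs from 54 to 63 m), so compare within a row, not with step 2.

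**5. How often the two analyses disagree.** Under the assumptions of step 2 and a normal approximation, the two test statistics correlate at √((1 + ρ)/2). If the true difference is 25 m, exactly one of them is significant in 7.5%, 5.8% and 3.2% of trials at ρ = 0.5, 0.7 and 0.9.

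**6. Hospital.** The documents give no between-hospital variation, and none of these figures includes a hospital effect. Any gain from adjusting for it is unquantified.

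**The case against.** The strongest reply is that the t-test is already the lead analysis in all but name. The endpoint is a change score, the t-test comes first in both places, the regression is an addition, and 10.5 reproduces as an unadjusted comparison. The test holds its level. One sentence naming it would close the labelling gap, keep the power basis and avoid changing the apparent lead analysis mid-trial, in an open-label study where an unblinded coordinator enters the 6MWD results (10.6.1, 10.6.3). This largely stands: the missing label alone would be missing detail. What it does not answer is why the deciding test should ignore the stratification factor and usually use baseline less well than a model the plan will fit anyway.

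A reader might infer an inflated type I error. If significance on either test counted, the error would be 7.3%, 6.8% or 6.0% at ρ = 0.5, 0.7 or 0.9 (bivariate normal, same correlation as in step 5). The plan states no such rule, so this is not its error rate and does not bear on severity.

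A reader might also infer that the plan means to report a covariate-selected model as its main result. The wording is about exploring, so the documents do not show that; they only fail to rule it out. Nor is it safe to call referral to ambulatory CR a constant. Section 10.4.11 says "all participants will receive a referral to ambulatory CR at time of discharge", but 5.1 allows enrolment up to 4 weeks after discharge, so for some participants that referral predates the study.

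**Conclusion.** The point holds as a recommended change, not as an error in the test or the sample size. The plan leaves the deciding analysis to inference, and the inferred one is valid but usually not the better of the two. The gain from switching is 6.4, 4.1 or 1.4 points of power at ρ = 0.5, 0.7 or 0.9, under assumed equal visit SDs and slopes. It can be nil if visit SDs differ and was −0.8 and −1.5 points in the two unfavourable slope cases. The documents cannot say where in that range the trial lies.

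The open covariate step applies to primary and secondary models alike. Its status needs stating, because neither section fixes the covariates, a threshold or the standing of a selected model.

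**What to change.** In 10.4.2 and the Protocol Summary:
- Name the regression of 3-month 6MWD on arm, baseline 6MWD and randomisation hospital, with heteroscedasticity-robust standard errors, as the single primary analysis. The endpoint stays change in 6MWD: with baseline in the model, regressing change gives the same arm coefficient.
- Optionally add an arm-by-baseline term, with baseline centred at its overall mean and that estimated mean allowed for in the standard error. This removes the possible large-sample loss under 3:1 allocation.
- Label the change-score t-test supportive.

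In 10.4.2 and 10.4.3, state that any model with covariates chosen by change-in-estimate is exploratory and cannot replace the main result.

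Use the hospital strata actually used at randomisation. Section 4.1 lists four and reports Yale enrolment as paused; 10.6.1 lists five, including Yale. Reconcile them and give a rule for pooling a very small stratum.

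In 10.5, keep the 90% and note that it was computed for the unadjusted change score. Date the amendment before any comparison of 6MWD by arm; 10.4.7 plans no formal interim analysis.

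Cost: an amendment with IRB approval (13.2), with no new data, visits or participants. It changes the apparent lead analysis mid-trial in an open-label study, so the dating matters. There may be a very small loss of precision if slopes differ by arm and the interaction term is left out.

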4.2 Study Endpoints

4.2.1 Primary Study Endpoints

Primary Efficacy Endpoint. The primary endpoint of this study is the change in the 6MWD between the baseline visit and 3-month follow-up visit. Change in 6MWD, reflective of functional capacity, is measured by the 6-minute walk test (6MWT). The 6MWT will be performed during baseline hospitalization and at the 3-month follow-up visit by a blinded research nurse or exercise therapist.

Primary Engagement Endpoint. Our main measure of engagement is weekly percent completion of the mHealth-CR program. Completion of mHealth-CR analyzed at weekly intervals will allow us to determine distinct engagement trajectories over the 3-month study period. Weekly engagement will be measured as the fraction of the following 11 elements completed each week: (1–7) daily entry of exercise data and RPE; (8) completed weekly phone call with exercise therapist; (9) at least one electronic communication with exercise therapist; (10) watching educational video (which will vary by week); and (11) at least one home BP measurement. Engagement will be assessed as a pseudo-continuous outcome, as the score can range from 0% (0 activities

CONFIDENTIAL

This material is the property of the NYU School of Medicine and Langone Medical Center. Do not disclose or use except as authorized in writing by the study sponsor

completed) to 100% (all 11 activities completed). We will also explore determination of a threshold for minimally sufficient engagement that is associated with improved outcomes.

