5.1 Inclusion Criteria

In order to be eligible to participate in this study, an individual must meet all of the following criteria:

1. Age ≥ 65 .
2. Currently hospitalized for AMI, PCI, or CABG **or**
Hospitalized for AMI, PCI or CABG within prior 4 weeks.
3. Capable of self-consent.
4. Understand and are able to perform study procedures (i.e. 6-minute walk test, use mHealth in English or Spanish).

Given logistical considerations, we expect that most participants with AMI and/or PCI will be recruited from the inpatient setting, with the baseline assessment taking place before discharge. However, given recent trends in AMI and PCI care (shorter hospital stays, including same-day discharge after PCI), we may not be able to capture all eligible participants at the time of hospitalization. In this case, the baseline study visit will take place at the first ambulatory cardiology visit (provided this occurs within 4 weeks of hospitalization). Since patients undergoing CABG have exposure to much greater physiologic stress as they recover from surgery, our expectation is that they will not be enrolled in the hospital (given inability to participate in mHealth-CR immediately after discharge), but instead will be enrolled at the first ambulatory visit (provided within 4 weeks of discharge). For patients with AMI or PCI, they can be enrolled either in the hospital or the first ambulatory visit (provided within 4 weeks of discharge).

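### The 6MWD analyses leave out index event and baseline setting, so differences in natural recovery cost some avoidable precision

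*Combined protocol and SAP*

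**What the plan says.** **Who is enrolled, and when.** Section 5.1 admits patients hospitalized for AMI, PCI or CABG, either currently or within the prior 4 weeks. It states: "For patients with AMI or PCI, they can be enrolled either in the hospital or the first ambulatory visit", the latter within 4 weeks of discharge. CABG patients are expected only at the ambulatory visit, and the reason given begins: "Since patients undergoing CABG have exposure to much greater physiologic stress as they recover from surgery". Section 7.1.1 sets follow-up at 3 months after the baseline assessment, so the clock starts at baseline and not at the event.

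**Where the baseline walk is done.** Section 4.2.1 says: "The 6MWT will be performed during baseline hospitalization and at the 3-month follow-up visit". Sections 2.3.1, 4.2.2 (safety endpoint), 10.4.4 and 10.6.1 (masking) also place it in hospital. Sections 5.1, 5.4 (enrollment) and 7.1.1 allow an outpatient baseline.

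**How 6MWD is analyzed.** Section 10.4.2 first gives an unequal-variance t-test on change scores. It then adds a regression of 3-month 6MWD on treatment, "with adjustment for baseline 6MWD and the stratification factor (enrollment site"). Other participant-level adjustment is exploratory and goes through a change-in-estimate criterion. Its examples are demographics and CR referral. Section 10.6.1 stratifies randomization by hospital only, and section 10.4.8 names sex, race and ethnicity as subgroups. Index event and baseline setting appear in none of these places.

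**The concern.** The change in 6MWD covers different stretches of recovery in different participants. Someone who walks 300 m before discharge and someone who walks 300 m four weeks later need not be heading for the same 3-month distance, yet a single baseline slope treats them alike. The t-test makes no allowance at all. Section 5.1 itself recognizes that recovery after CABG differs, and section 10.5 expects about 35 m of improvement in controls, more than the 25 m target difference. Untreated recovery is therefore not negligible in this trial.

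At stake is precision. Spread in recovery that is unrelated to treatment goes into the standard error. With only about 80 evaluable controls and no stratification on these factors, chance imbalance passes into the estimate.

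The exploratory step is a weak safeguard. It looks for a shift in the estimate, not a gain in precision, and it picks covariates after the effect has been seen.

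**Working it through.** **Inputs from section 10.5.** "Assuming a conservative standard deviation estimate of 60 meters"; 240 v 80 evaluable; "using a two-sided, 0.05-level test"; control improvement about 35 m.

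**1. The plan's own figures.** SE = 60 × √(1/240 + 1/80) = 60 × 0.1291 = 7.75 m. Power at 25 m = Φ(25/7.75 − 1.96) = 89.8% (noncentral t: 89.6%). The plan says: "320 participants provide approximately 90% power to detect a difference between groups of 25 meters". At 22 m the result is 81.1%, against a stated 80% for a difference "between groups as small as 22 meters". Both reproduce.

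**2. Cost to the t-test on change.** The documents give no recovery figure by setting or event, so these are assumptions: a share q = 0.5 of baselines in hospital, a gap g between settings in mean natural change, and 60 m as the within-setting SD. Total SD = √(60² + q(1−q)g²), and SE = SD × 0.1291.

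| g (m) | SD (m) | SE (m) | Power at 25 m |
|---|---|---|---|
| 0 | 60.0 | 7.75 | 89.8% |
| 20 | 60.8 | 7.85 | 88.9% |
| 40 | 63.2 | 8.16 | 86.5% |
| 60 | 67.1 | 8.66 | 82.3% |
| 80 | 72.1 | 9.31 | 76.6% |

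**3. The same loss seen as chance imbalance.** The SD of the difference between arms in group share is √(q(1−q)) × 0.1291, which is 5.2 to 6.5 percentage points for q = 0.2 to 0.5. At g = 40 m this moves the unadjusted difference by an SD of 2.1 to 2.6 m, a 95% range of about ±4 to ±5 m. It is not an extra loss: 7.75² + 2.58² ≈ 8.16².

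**4. What a setting covariate adds to the regression.** Suppose in-hospital starters walk g less at baseline and reach the same 3-month mean. Write s for the within-setting SD of 6MWD (80 to 100 m, assumed).

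- *Equal baseline and follow-up SD.* A change SD of 60 m gives r = 1 − 1800/s². Residual variance with setting is s²(1 − r²). Without setting it is s² − (r·s²)²/(s² + g²/4).
  - g = 40, s = 80: r = 0.719, residual SD 57.3 falls to 55.6, power 92.2% rises to 93.6%.
  - g = 40, s = 100: r = 0.82, residual SD 59.5 falls to 57.2, power 90.3% rises to 92.3%.
  - g = 20: the gain is about 0.4 to 0.5 point.
- *Within-group baseline slope of 1* (the case least favorable to the planned regression). Residual variance without setting is 3600 + s²(g²/4)/(s² + g²/4), and with setting it is 3600.
  - g = 40, s = 90: residual SD 63.1 falls to 60.0, power 86.6% rises to 89.8%.
  - g = 20: the gain is about 0.8 point.

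The gain is therefore under 1 point at 20 m and about 1.4 to 3 points at 40 m.

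**5. Check on large gaps.** With q = 0.5 and mean control recovery of 35 m, later starters recover 35 − g/2. That is 25 m at g = 20 and 15 m at g = 40, but only 5 m at g = 60 and −5 m at g = 80.

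**6. If 60 m already contains the mixture.** Removing it leaves √(60² − q(1−q)g²): 59.2 m at g = 20 (power 90.5%) and 56.6 m at g = 40 (power 92.8%).

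**The case against.** Several points against the concern stand.

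- The planned regression already recovers much of the loss. With equal baseline and follow-up SDs it gives about 90-92% at a 40 m gap without any setting term. Site is in the model too, and may partly stand in for setting.
- Gaps of 60 to 80 m, which produce the striking losses, would leave later starters with almost no recovery or a decline. That fits poorly with the plan's 35 m.
- The direction of the gap is not established. CABG patients start late and may have the most recovery still to come, which would shrink or reverse it. The calculation uses one binary setting and does not model index event.
- Section 10.5 calls 60 m conservative and does not say whether it is a within-setting figure.

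A reader might infer that the primary comparison is biased, or that true power is nearer 76%. The documents support neither. Randomization protects the comparison and the test keeps its level. The 76.6% figure needs an 80 m gap and applies only to the unadjusted t-test.

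What remains is that neither factor is prespecified, that both are known for every participant, and that on none of these readings does adjusting for them do material harm. Adding covariates to the regression also leaves the t-test untouched, so the fix has to say which analysis is primary.

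**Conclusion.** The point holds as a modest, avoidable loss of precision. Assuming half of baselines in hospital and a within-group SD of 60 m, a 20 to 40 m recovery gap takes change-score power at 25 m from 90% to 89-86%, and a setting covariate gains the regression up to about 3 points. Larger gaps would cost more but are hard to square with the plan's own control recovery. If 60 m already includes the spread, nothing is lost against the stated power, and adjustment raises it above 90%. The true size cannot be settled from the documents, and the sample-size arithmetic is correct.

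Separately, the documents contradict themselves on where the baseline walk takes place. That needs resolving whatever the recovery gap turns out to be.

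**What to change.** In section 10.4.2:

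- Name the baseline-adjusted regression as the primary 6MWD analysis, with the t-test on change as supportive.
- Prespecify in it, alongside baseline 6MWD and site, index event (AMI, PCI without AMI, CABG) and baseline setting (in hospital v after discharge), or days from event to baseline walk in place of setting. State how patients with more than one event are classified, since section 2.3.1 notes that AMI patients may undergo PCI or CABG.
- Fix these covariates before unblinded data are seen, and keep them outside the change-in-estimate step.

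Reconcile sections 2.3.1, 4.2.1, 4.2.2, 10.4.4 and 10.6.1 (baseline walk in hospital) with sections 5.1, 5.4 and 7.1.1 (outpatient baseline allowed).

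The cost is document wording and about three model degrees of freedom out of about 320. No new data are needed, because eligibility requires the index event and the baseline visit is already dated. Index event and setting will overlap, since CABG patients are expected only as outpatients. The setting term will therefore be estimated mainly within AMI and PCI patients.
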